7.5 Analysis of Safety

All analysis of safety will be presented by treatment group for the SAF.

7.5.1 Treatment Emergent Adverse Events

The coding dictionary for this study will be MedDRA Version 16.

TEAE is defined as an adverse event observed after the first study drug injection (Day 1) through Day 380. If the adverse event occurs on Day 1 and the onset check box is marked “Onset after first dose of study drug” or the onset check box is left blank, then the adverse event will be considered treatment emergent. If the adverse event occurs on Day 1 and the onset check box is marked “Onset before first dose of study drug”, then the adverse event will not be considered treatment emergent. If a subject experiences an event before the first study drug injection and continues during the primary study period, the event will be considered as TEAE only if it has worsened in severity during the primary study period (i.e., it is reported with a new start date).

An overview summary table will include the following:

- Number and percentage of subjects with TEAEs,
- Number and percentage of subjects with drug related TEAEs,
- Number and percentage of subjects with serious TEAEs,
- Number and percentage of subjects with serious drug related TEAEs,
- Number and percentage of subjects with TEAEs leading to permanent discontinuation of study drug injection, and
- Number and percentage of subjects with drug related TEAEs leading to permanent discontinuation of study drug injection, and
- Number of deaths.

The number and percentage of subjects with TEAEs, as classified by SOC and PT will be summarized for each treatment group. Summaries will be provided for:

- TEAEs
- drug related TEAEs,
- serious TEAEs,
- drug related serious TEAEs,
- TEAEs leading to permanent discontinuation of study drug,
- drug related TEAEs leading to permanent discontinuation of study drug,
- TEAEs excluding serious adverse events that equal to or exceed a threshold of 5.0% in any treatment group, and
- common TEAEs that equal to or exceed a threshold of 5.0% in any treatment group.

Drug-related AE is defined as any AE with at least possible relationship to study treatment as assessed by the investigator or with missing assessment of the causal relationship. AEs will be graded using National Cancer Institute (NCI)-Common Terminology Criteria for Adverse

Event (CTCAE) guidelines version 4.03. There are five grades: 1=mild, 2=moderate, 3=severe, 4=life threatening, 5=death. Missing severity will not be imputed.

The number and percentage of subjects with TEAEs, as classified by PT only, will be summarized for each treatment group.

TEAEs and the number and percentage of subjects with TEAEs, as classified by SOC and PT will also be summarized by severity and by relationship to study drug. If an adverse event changes in severity or relationship, then the subject will be counted only once with the worst severity and highest degree of relationship. Drug related TEAEs will be presented in a similar way by severity.

7.5.2 Adverse Events of Special Interest

The number and percentage of subjects with each protocol defined grade will be summarized by treatment group for each injection visit and for worst grades across visits unless specified otherwise. There should be no imputations for missing values.

7.5.2.1 Acute Local Reactions Assessed by Investigator and Subject

The symptoms of local vaccine reactions and severity grading are defined below:

Local Reaction To Injectable Product	Mild (Grade 1)	Moderate (Grade 2)	Severe (Grade 3)	Potentially Life -Threatening (Grade 4)
Pain	Does not interfere with activity	Repeated use of non-narcotic pain reliever > 24 hours or interferes with activity	Any use of narcotic pain reliever or prevents daily activity	Emergency room (ER) visit or hospitalization
Tenderness	Mild discomfort to touch	Discomfort with movement	Significant discomfort at rest	ER visit or hospitalization
Erythema/Redness *	2.0 – 5 cm	5.1 – 10 cm	> 10 cm	Necrosis or exfoliative dermatitis
Induration / Swelling **	2.0 – 5 cm and does not interfere with activity	5.1 – 10 cm or interferes with activity	> 10 cm or prevents daily activity	Necrosis

Local reactions assessed by subjects:

Each subject will take 7 day diaries post each injection to record the symptoms and the corresponding grades as shown above. For each symptom the maximum grade of the 7 day diary associated with each injection visit will be defined as the symptom grade for that visit.

Local reactions assessed by investigators:

Symptoms are assessed one hour post each injection by investigators and the results are captured in the CRFs.

7.5.2.2 Acute Systemic Reactions Assessed by Subjects

The symptoms and grading of systemic vaccine reactions assessed by subjects are defined below:

Systemic (General)*	Mild (Grade 1)	Moderate (Grade 2)	Severe (Grade 3)	Potentially Life –Threatening (Grade 4)
Fatigue	No interference with activity	Some interference with activity	Significant; prevents daily activity	ER visit or hospitalization
Myalgia	No interference with activity	Some interference with activity	Significant; prevents daily activity	ER visit or hospitalization
Fever (°C)*** (°F)***	38.0-38.4 100.4-101.1	38.5-38.9 101.2-102.0	39.0-40 102.1-104	> 40 > 104

Each subject will take 7 day diaries post each injection to record the grades associated with fatigue and myalgia and record the temperatures based on which the protocol defined grade will be derived according the above table. For each symptom the maximum grade of the 7 day diary associated with each injection visit will be defined as the symptom grade for that visit.

7.5.2.3 Acute Systemic Reactions Assessed by Investigators

The symptoms and grading of systemic vaccine reactions assessed by investigators are defined below.

Vital signs are assessed pre- and 1 hour post- each injection. Changes will be used to determine the grades 1-3 according to the charter below. Grade 4 (except for fever related) comes from the SAEs. If any SAE that is considered related to systemic reactions post each injection by the investigators (captured in the CRF) and meets one of the two criteria below will be a grade 4 systemic reaction: (1) PT=Endotracheal Intubation, or (2) PT= Tachycardia, Bradycardia, Hypertension, or Hypotension with NCI- CTCAE v4.03 severity grade \geq 4.

Systemic (General)*	Mild (Grade 1)	Moderate (Grade 2)	Severe (Grade 3)	Potentially Life-Threatening (Grade 4)
Fever (°C)*** (°F)***	38.0-38.4 100.4-101.1	38.5-38.9 101.2-102.0	39.0-40 102.1-104	> 40 > 104
Tachycardia-beats per minute	Increase in heart rate 5-15 beats/minute	Increase in heart rate 16-30 beats/minute	Increase in heart rate > 30 beats/minute	ER visit or hospitalization for arrhythmia
Bradycardia-beats per minute	Decrease in heart rate 5-10 beats/minute	Decrease in heart rate 11-15 beats/minute	Decrease in heart rate > 15 beats/minute	ER visit or hospitalization for arrhythmia
Hypertension (systolic)-mm Hg	Increase in systolic blood pressure (SBP) 20-30 mmHg	Increase in SBP 31 mmHG - 40 mmHg	Increase in SBP > 40 mmHg	ER visit or hospitalization for malignant hypertension
Hypotension (systolic)-mm Hg	Decrease in SBP 5 mmHg	Decrease in SBP 5.1 mmHg to 10.0 mmHg	Decrease in SBP to > 10.0 mmHg	ER visit or hospitalization for hypotensive shock
Respiratory Rate-breaths per minute (at rest)	17-20	21-25	> 25	Intubation

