5.4.1 Vital Signs

Vital signs (systolic and diastolic blood pressure, pulse rate, respiratory rate and temperature) will be collected at all dosing visits, and at Screening (V1), and at V12 and 13. Height will be collected at Screening only. Weight will be collected at V1, V2 and Study Completion (V13).

Vital signs will be collected as follows:

- Vital signs will be collected immediately prior to injection, at 15 and 60 minutes post Study Drug injection at study visits accompanied by injection.
- Vital signs will be collected once at Screening (Visit 1), and at Visits 12 and 13.

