5.4.4 Systemic Reactogenicity Assessments

Specific signs of systemic reactogenicity will be evaluated one hour after each injection (Appendix 5). The subject must be in direct view of the clinic staff for 15 minutes following each injection, then remain in the clinic area for an additional 45 minutes for evaluation of systemic reactogenicity. Vital signs, including temperature, pulse, respiration and blood pressure will be collected just prior to injection, 15 minutes post-injection and at one hour post-injection. Using the pre-injection vital signs as baseline, if a post Study Drug injection vital sign meets Grade 1-4 criteria per Appendix 5, it is to be repeated and confirmed within 5 minutes of first assessment. Systemic measurements that will be followed for 7 days are fever, fatigue and myalgia.

Grading of reactogenicity will be done using the protocol-specified reactogenicity scale (Appendix 4) and the NCI-CTCAE v. 4.03 grading scale. The daily maximum measurement of systemic reactogenicity signs and symptoms will be recorded.

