Sites that are determined to have an unacceptable assay in their local lab but are able to determine a Sponsor- deemed acceptable work practice flow for utilizing another acceptable local assay or methodology will be allowed to participate in the trial. Note: Local CMV plasma viral load testing may be performed only at a local laboratory approved by the Sponsor.

Subjects will be followed for one year after first Study Drug injection (Primary Study completion/Day 395) for CMV viremia, CMV syndrome, CMV tissue-invasive disease, CMV-specific AVT, graft survival and subject survival.

Subjects will be followed for one year after the first Study Drug injection for resistance to valganciclovir or ganciclovir. Viral resistance will be assessed by a Central lab when there is no reduction in viral load two weeks after initiating valganciclovir/ganciclovir, when there is

no improvement in clinical signs and symptoms two weeks after initiating valganciclovir/ganciclovir or any time resistance to any CMV-specific AVT is suspected by the Investigator.

Immunogenicity to pp65 and gB will be assessed prior to Dose 1, two weeks after Dose 2, prior to Dose 3, two weeks after Dose 4, prior to Dose 5 and at the last study visit.

Subjects will be evaluated for local and systemic reactogenicity 15 minutes and one hour after each Study Drug injection and for 7 days by subject reporting via diary after each Study Drug injection.

Subjects will be contacted by telephone at 6 months after Day 395, then annually for the next 4 years to evaluate long-term safety related to the DNA vaccine. Items to be assessed by questionnaire and available patient records include mortality, development of any new malignancies, development of infection requiring hospitalization or resulting in death, graft survival, creatinine, and erythema and/or induration at the injection sites.

All adverse events (AEs) and serious adverse events (SAEs) will be collected from signing of the informed consent through one year post Study Drug injection. AEs occurring from signing of informed consent until just prior to the first dose of Study Drug, should be reported as a change in medical status or medical history. SAEs from the time of signing the informed consent will be recorded on the SAE worksheet and reported per Section 5.5.6. AEs reported after the first dose will be reported on the AE eCRF.

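### SAP 7.5.2.3 grades investigator-assessed systemic reactions from the 1-hour vital signs only, leaving out the 15-minute readings, and its Grade 4 text and table differ in four of six rows

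*SAP*

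**What the plan says.** SAP 7.5.2.3 opens its derivation with "Vital signs are assessed pre- and 1 hour post- each injection", and continues: "Changes will be used to determine the grades 1-3 according to the charter below". It gives no rule for a 15-minute value or for choosing between two post-injection values. SAP 7.5.2 says the tables report the protocol-defined grade for each injection visit and the worst grade across visits.

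The protocol schedule is fuller. Section 5.4.1: "Vital signs will be collected immediately prior to injection, at 15 and 60 minutes post Study Drug injection at study visits accompanied by injection". Section 5.4.4 says vital signs "will be collected just prior to injection, 15 minutes post-injection and at one hour post-injection", and then that "if a post Study Drug injection vital sign meets Grade 1-4 criteria per Appendix 5, it is to be repeated and confirmed" within 5 minutes. It also says that the daily maximum of systemic signs and symptoms is recorded. SAP 3.2 agrees on the times: "Subjects will be evaluated for local and systemic reactogenicity 15 minutes and one hour after each Study Drug injection". So does the reactogenicity footnote to the SAP's schedule of assessments.

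On Grade 4, the table in SAP 7.5.2.3 repeats protocol Appendix 5. The hypotension cell, for example, reads "ER visit or hospitalization for hypotensive shock". The text above the table takes Grade 4, fever apart, from SAEs that the investigator relates to a systemic reaction. Such an SAE must be either endotracheal intubation, or one of four preferred terms (tachycardia, bradycardia, hypertension, hypotension) with CTCAE grade 4 or higher.

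**The concern.** A programmer who follows SAP 7.5.2.3 will calculate changes at one hour and leave the 15-minute readings unused. A rise in heart rate or a fall in blood pressure that is present at 15 minutes and gone by 60 would then have no grade in a table meant to show protocol-defined grades. Other outputs do not clearly recover it. SAP 7.5.4 gives only summary statistics by visit, and SAP Appendix 4 records that the summary of potentially significant vital signs was removed. Appendix 4 offers no reason for leaving out the 15-minute readings.

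The Grade 4 issue is one of definition. The same event can be Grade 4 by the table and not by the text, so the reported count depends on which is programmed. Safety is one of the trial's two objectives, and a Grade 4 systemic reaction is also a treatment-discontinuation criterion in protocol 6.1.1. The reported Grade 4 counts should therefore mean what Appendix 5 says.

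**Working it through.** The plan states no figure to reproduce. The check compares the texts, counts scheduled readings, and works one illustration of the fix's downside.

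**Readings used.** Injections per subject: 5 (SAP 3.2). Post-injection readings per injection: 2 in protocol 5.4.1 and 1 in SAP 7.5.2.3.

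- Protocol: 5 × 2 = 10 sets per fully dosed subject.
- SAP derivation: 5 × 1 = 5 sets.
- Share not graded: 5 / 10 = one half. With 140 fully dosed subjects, 140 × 10 = 1,400 against 140 × 5 = 700.

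This counts scheduled readings, not missed reactions.

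**Grade 4, row by row.**

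| Row | Table | Text | Same rule? |
|---|---|---|---|
| Fever | Temperature threshold | Exempt from the SAE rule | Yes |
| Tachycardia, bradycardia | ER visit or hospitalization for arrhythmia | Related SAE, named term, CTCAE 4 or higher | No (2 rows) |
| Hypertension | ER visit or hospitalization for malignant hypertension | As above | No |
| Hypotension | ER visit or hospitalization for hypotensive shock | As above | No |
| Respiratory rate | Intubation | Related SAE of endotracheal intubation | Broadly |

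Four of six rows differ. Two mismatches follow from the documents alone:

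1. Protocol 5.5.3 lists inpatient hospitalization as an SAE criterion but not an ER visit as such. An ER visit not judged serious on other grounds meets the table and fails the text.
2. An arrhythmia or shock coded to a preferred term outside the four meets the table and fails the text.

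In the other direction, the text does not require an ER visit or hospitalization at all.

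**Cost of using two readings.** The hypotension row grades any fall in systolic pressure of 5 mmHg or more, and a fall over 10 mmHg is Grade 3. The documents give no variability. Assume, for illustration, normally distributed changes with mean zero, SD 6 to 12 mmHg, and correlation 0.3 to 0.7 between the two readings. For one reading p = Φ(−c/SD); for either of two, 2p − P(both).

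- Fall of 5 or more: 20-34% with one reading, 29-52% with the worse of two.
- Fall over 10: 5-20% with one reading, 8-34% with the worse of two.

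These chance rates would apply equally to both arms.

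**The case against.** The strongest reply is that the protocol is not uniform. Section 5.4.4 begins "Specific signs of systemic reactogenicity will be evaluated one hour after each injection (Appendix 5"), and the sentence applying Appendix 5 to post-injection readings is a trigger for a confirmatory repeat, not an analysis rule. On that view the SAP follows one of the protocol's statements. This part stands: the SAP omits the 15-minute readings by description rather than by express exclusion, and the departure is from a mixed text. But the same paragraph collects the 15-minute readings, grades any post-injection value and records the daily maximum, and SAP 3.2 names both times. One hour alone is the weaker reading.

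A second reply is that taking the worse of two readings adds noise, as the illustration shows. That is true and should be stated with the results. It does not defeat the change, because the protocol already calls for the daily maximum and SAP 7.5.2.2 already uses the maximum grade for diary symptoms.

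A reader might go further in three ways that the documents do not support.

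- That acute reactions are lost from the safety reporting. An abnormality that causes symptoms, needs intervention or is clinically significant is an adverse event under protocol 5.5.1 and would reach the TEAE tables. Diary fever, fatigue and myalgia are unaffected.
- That the omitted readings fall when reactions are most likely. No passage gives the timing of vital-sign reactions.
- That a hospitalization graded CTCAE 3 shows the Grade 4 conflict. This depends on CTCAE criteria not in the documents. Protocol 5.5.5 places hospitalization at Grade 3 only for items that CTCAE does not cover.

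**Conclusion.** The point holds as an inconsistency that should be corrected. Following SAP 7.5.2.3 literally leaves half of the scheduled post-injection vital-sign sets out of the grading, so a transient 15-minute abnormality gets no grade in the reactogenicity table. How many subjects' grades would change cannot be estimated, because the documents give no reaction rates or variability. The Grade 4 text and table conflict in four of six rows, and the two mismatches shown need no outside source.

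The effect is limited to one descriptive safety table. The primary efficacy analysis is untouched. Discontinuation under protocol 6.1.1 rests on grades confirmed by a health care professional, not on this derivation. The conclusion assumes that the programming follows 7.5.2.3 as written.

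**What to change.** In SAP 7.5.2.3, state that vital signs are taken before injection and at 15 and 60 minutes after it, and that each sign is graded per injection by the maximum grade over the two post-injection readings relative to the pre-injection value. The fever and respiratory-rate rows are absolute values, so there the grade comes from the reading itself. State how the 5-minute confirmatory repeat enters: whether an unconfirmed reading counts, and which value is graded. Note in the report that two readings give more chance findings in both arms: low grades and, in the hypotension row, some Grade 3.

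Reconcile the Grade 4 text with the Grade 4 column and protocol Appendix 5 so that one definition is programmed. Which clinical threshold that should be is for the sponsor's medical team and is not judged here.

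The cost is SAP wording and a small change to the derivation, made before unblinding, on data the protocol already collects.

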12.5 Appendix 5: Grading of Signs of Systemic Reactogenicity

Systemic (General)*	Mild (Grade 1)	Moderate (Grade 2)	Severe (Grade 3)	Potentially Life-Threatening Grade 4)
Fatigue	No interference with activity	Some interference with activity	Significant; prevents daily activity	ER visit or hospitalization
Myalgia	No interference with activity	Some interference with activity	Significant; prevents daily activity	ER visit or hospitalization
Vital Signs**†				
Fever (°C)*** (°F)***	38.0-38.4 100.4-101.1	38.5-38.9 101.2-102.0	39.0-40 102.1-104	> 40 > 104
Tachycardia-beats per minute	Increase in heart rate 5-15 beats/minute	Increase in heart rate 16-30 beats/minute	Increase in heart rate > 30 beats/minute	ER visit or hospitalization for arrhythmia
Bradycardia-beats per minute	Decrease in heart rate 5-10 beats/minute	Decrease in heart rate 11-15 beats/minute	Decrease in heart rate > 15 beats/minute	ER visit or hospitalization for arrhythmia
Hypertension (systolic)-mm Hg	Increase in systolic blood pressure (SBP) 20-30 mmHg	Increase in SBP 31 mmHG - 40 mmHg	Increase in SBP > 40 mmHg	ER visit or hospitalization for malignant hypertension
Hypotension (systolic)-mm Hg	Decrease in SBP 5 mmHg	Decrease in SBP 5.1 mmHg to 10.0 mmHg	Decrease in SBP to > 10.0 mmHg	ER visit or hospitalization for hypotensive shock
Respiratory Rate-breaths per minute (at rest)	17-20	21-25	> 25	Intubation

* Grading of Systemic Reactogenicity.

**Subject should be at rest for all vital sign measurements.

***Oral temperature; no recent hot or cold beverages or smoking.

†Pre- dosing vital signs are to be used as baseline values for determining changes post Study Drug Injection.

Reference: Modified for the Renal Transplant Population from the Guidance for Industry titled “Toxicity Grading Scale for Healthy Adult and Adolescent Volunteers Enrolled in Preventive Vaccine Clinical Trials” issued by FDA on September 2007.

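### The respiratory-rate row of the systemic-reaction scale grades absolute values, although the SAP says grades come from change, so an unchanged rate can be counted as a reaction

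*SAP*

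**What the plan says.** SAP 7.5.2.3 names the readings ("Vital signs are assessed pre- and 1 hour post- each injection") and the rule ("Changes will be used to determine the grades 1-3 according to the charter below"). Protocol Appendix 5 attaches a footnote to the vital-signs part of the same scale; it says that the readings taken before dosing (pre-) "dosing vital signs are to be used as baseline values for determining changes post Study Drug Injection".

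The table below that rule mixes two kinds of row:

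- **Heart rate and systolic pressure:** graded on the increase or decrease.
- **Respiratory rate at rest:** graded on the value itself, with 17-20 as Grade 1, 21-25 as Grade 2 and above 25 as Grade 3. Nothing refers to a change.
- **Fever:** also graded on the value itself. However, Protocol 5.1.1 bars the injection at 38 °C or above.

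On reporting, SAP 7.5.2 says: "The number and percentage of subjects with each protocol defined grade will be summarized by treatment group". This is done for each injection visit and for the worst grade across visits.

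Protocol 5.4.4 asks for two scales: "Grading of reactogenicity will be done using the protocol-specified reactogenicity scale (Appendix 4) and the NCI-CTCAE v. 4.03 grading scale". (The systemic scale is in fact in Appendix 5.) It also requires a post-injection vital sign that meets a grade to be repeated and confirmed within five minutes. SAP 7.5.2.3 does not say whether the first or the confirmed reading is graded.

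**The concern.** The rule and the row cannot both be followed. If the programmer follows the table, a subject whose rate was already 17 or more before dosing, and has not moved, is reported as having a systemic reaction. If the programmer follows the sentence, the row gives no change thresholds and cannot be applied. Two competent programmers could produce different safety tables from the same data.

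Safety is one of the trial's two objectives, and these tables would supply the reaction rates reported for the vaccine. Background readings counted as reactions raise the rate in both arms and shrink the visible difference. Taking the worst grade over five injections adds to the effect.

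**Working it through.** **Step 1: what needs no outside figure.** Take a subject at 18 breaths per minute before and after injection.

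- By the sentence in SAP 7.5.2.3 and the Appendix 5 footnote: change = 18 − 18 = 0, so no reaction.
- By the table: 18 lies in 17-20, so Grade 1.

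**Step 2: do the safeguards catch it?**

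- *Pre-dose gate.* A raised temperature blocks the injection, so a pre-existing fever should not be graded afterwards. Protocol 5.1.1 sets no such condition for respiratory rate.
- *Five-minute repeat.* The repeat confirms the post-injection value. A subject who is steadily at 18 is confirmed at 18.

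**Step 3: size, under stated assumptions.** The documents give no expected reaction rate and no distribution of respiratory rate, so there is no plan figure to reproduce. Assume no vaccine effect, whole-number readings, a normal resting rate with mean 14, 16 or 18 and SD 2 or 3, and half of the variance between subjects.

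P(graded) = P(reading ≥ 17) = 1 − Φ((16.5 − mean)/SD)

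- Mean 14: 1 − Φ(1.25) = 11% at SD 2; 1 − Φ(0.83) = 20% at SD 3.
- Mean 16: 1 − Φ(0.25) = 40% at SD 2; 1 − Φ(0.17) = 43% at SD 3.

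The other columns use simulated pre- and post-injection pairs, or five visits per subject. The last column is the product of the second and third.

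| Mean (SD 2 / SD 3) | Readings graded | Of these, no rise from pre-dose | Subjects graded at least once in 5 visits | All readings graded with no rise |
|---|---|---|---|---|
| 14 | 10.6% / 20.3% | 23.1% / 27.2% | 31% / 49% | 2.4% / 5.5% |
| 16 | 40.2% / 43.2% | 39.2% / 37.6% | 75% / 78% | 15.8% / 16.2% |
| 18 | 77.3% / 69.1% | 52.4% / 46.6% | 97% / 94% | 40.5% / 32.2% |

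A reading with no rise cannot exceed its own pre-dose grade, so a rule based on exceeding that grade removes every one of them. It also removes rises that stay within one band. It does not remove chance movements that cross a band.

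**Step 4: effect on the contrast.** Let b be the background share graded in both arms, and d the true share reacting on vaccine only, independent of the background. The visible difference is [b + (1 − b)d] − b = d(1 − b). With d = 15% as an illustration:

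- b = 5%: 0.15 × 0.95 = 14.3 points.
- b = 40%: 0.15 × 0.60 = 9.0 points.
- b = 50%: 0.15 × 0.50 = 7.5 points.

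**The case against.** **The governing sentence and the footnote may settle it.** The footnote sits on the vital-signs header, which covers respiratory rate. Read that way, an unchanged value is no reaction. This stands in part: a reader might infer that the 18-and-18 subject will certainly be tabulated as Grade 1, but the documents show only that the table says so while the rule says otherwise. It does not remove the problem, because the rule supplies no thresholds for this row.

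**The consequence is modest.** This stands. Both arms are graded by the same rule in a blinded trial, so there is no directional bias. The SAP specifies no test on these tables. Under Protocol 6.1.1, a Grade 3 respiratory or systolic reading alone is not among the listed reasons for stopping study treatment.

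**Other tables help.** A reader might infer that nothing offsets the inflated grades. That is too strong. SAP 7.5.1 tabulates CTCAE-graded adverse events by severity and relationship, and Protocol 5.5.1 keeps harmless vital-sign shifts out of them. SAP 7.5.4 summarises vital signs and their change. However, its baseline is the last value on or before the first injection, so it does not give the pre-to-post change at doses 2 to 5.

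**Grading is not tabulating.** Protocol 5.4.4 requires grading on both scales and does not require side-by-side tables. That is correct. But for these vital signs SAP 7.5.2.3 uses CTCAE severity only in defining some Grade 4 reactions, so the second grading is otherwise not shown in the acute-reaction tables.

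**Conclusion.** The contradiction between the change rule and the respiratory-rate row is established from the text alone. Its likely effect is an inflated rate of respiratory-rate reactions in both arms and a weaker vaccine-placebo contrast in that table, without bias.

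The size rests on assumed resting rates. The share of readings graded runs from 11-20% at mean 14 to 40-43% at mean 16 and 69-77% at mean 18. The share of graded readings that show no rise is 38-39% at mean 16, and 23-52% across the three means.

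A reader might extend the point to systolic pressure, where a rise is ungraded below 20 mmHg but a fall of more than 10 is Grade 3. The documents do not support calling that an error. Those rows are change-based, agree with the rule, and belong to a scale that Appendix 5 describes as adapted for renal transplant recipients. Different cut-offs for rises and falls are a grading choice. Chance counts there also depend heavily on which reading is used. With an assumed SD of change of 10 mmHg and five independent visits, Grade 3 falls would occur by chance in 55% of subjects on first readings. If only confirmed readings count, with half of the variance shared between the two readings, the figure is 25%.

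One wording fault remains in that row: "Decrease in SBP to > 10.0 mmHg" does not parse as written, while the Grade 2 band, "Decrease in SBP 5.1 mmHg to 10.0 mmHg", indicates that the size of the fall is meant.

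**What to change.** In SAP 7.5.2.3:

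1. Count a respiratory-rate reaction only when the post-injection grade exceeds the grade of the same subject's pre-injection reading at that visit.
2. State whether the first or the confirmed repeat reading is graded, for all vital signs.
3. Tabulate the NCI-CTCAE grade for these signs as well as the protocol grade, since Protocol 5.4.4 has both assigned.
4. Show the pre-to-post change in systolic pressure by arm at each injection.
5. Reconcile the wording of the Grade 3 hypotension cell with the Grade 2 band, in the SAP and in Protocol Appendix 5.

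The cost is SAP text and programming, plus the wording correction in the protocol appendix. Pre-injection readings are already collected at every dosing visit, and Protocol 5.4.4 already calls for CTCAE grading. No threshold used for care or for stopping treatment needs to change. The rule should be fixed before unblinding.
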